8.1.5 Subgroup Analyses

Subgroup analyses of change from baseline in ZAN-BPD Total Score to every study week in the double-blind treatment period will be performed by the following factors:

- Sex (Based on the biological status)
- Race (White and All Other Races)
- Age group (Age<55 and Age≥55)
- Region (North America and Europe)
- Status of Background ADT (With ADT and Without ADT)

All subgroup analyses will be conducted using the same MMRM analysis as for the primary efficacy analysis except that the fixed class effect term for trial center will not be included in the model

Interaction effects of treatment-by-subgroup will be assessed at Week 10 for the subgroups identified in the previous paragraph. The same MMRM model will be used as for the primary efficacy analysis with the addition of terms for subgroup-by-week and treatment-by-subgroup-by-week. These treatment-by-subgroup interaction analyses will be presented in statistical documentation.

8.2 Key Secondary Endpoint Analysis

The key secondary efficacy endpoint is the change from baseline to Week 10 in the double-blind treatment period in CGI-S score. This endpoint will be analyzed by fitting the similar MMRM model described in the primary analysis.

This endpoint will be analyzed by similar analysis described in Section 8.1.4.3 to evaluate the impact of COVID.

8.3 Control of Experiment-wise Type 1 Error

To control the family-wise type I error when testing for both the primary efficacy endpoint and the key secondary efficacy endpoint, a stepwise hierarchical testing procedure is applied. The statistical testing will be performed in the following order. The statistical test between brexpiprazole and placebo group for an endpoint after the first one will be performed only when the nominal p-value reaches significance level at 0.05 (2-sided) for all the preceding endpoints:

- 1) Primary efficacy endpoint based on the FAS for Enriched Subjects
- 2) Key secondary endpoint based on the FAS for Enriched Subjects
- 3) Primary efficacy endpoint based on the FAS
- 4) Key secondary endpoint based on the FAS

[figure not shown]
8.4 Secondary Efficacy Endpoint Analysis

[figure not shown]
Secondary efficacy endpoints are as follows:

- 1) Change from baseline in the Patient's Global Impression of Severity (PGI-S) to each trial visit during the double-blind treatment period
- 2) Patient's Global Impression of Change (PGI-C) score at each trial visit during the double-blind treatment period

3) Clinical Global Impression-Improvement of Illness (CGI-I) score at each trial visit during the double-blind treatment period

Variable (1) will be evaluated using the same MMRM model described in the primary analysis. Variables (2) and (3) will be evaluated by the Cochran-Mantel-Haenszel (CMH) Row Mean Score Differ Test controlling, in last-observation-carried-forward (LOCF) analysis, for trial center.

9 Safety Analysis

Standard safety variables to be analyzed include AEs, clinical laboratory tests, vital signs, ECGs, and physical examinations. In addition, data from the following safety scales will be evaluated: assessments of suicidality (C-SSRS) and EPS (eg, the SAS, AIMS, and BARS). Safety analysis will be conducted based on the Safety Sample defined in Section 5.1. In general, baseline of a safety variable is defined as the last observation of the variable before taking the first dose of IMP, unless specified otherwise. Prospectively defined criteria will be used to identify potentially clinically relevant abnormal values for clinical laboratory tests, vital signs, ECGs, and body weight.

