Screening/Other: SCID-5-PD, Mini International Neuropsychiatric Interview (MINI) for Psychotic Disorders, medical history, psychiatric history (including BPD history and BPD therapy), urine drug screen/blood alcohol test, and urine pregnancy test.

Data Monitoring Committee: None

Statistical Methods:

In general, descriptive statistics will be provided for all efficacy and safety endpoints. Continuous variables will be summarized by tabulations of mean, median, range, and standard deviation (SD). Tabulations of frequency distributions will be provided for categorical variables. The change from baseline in the ZAN-BPD total score will be analyzed using a mixed-effect model repeated measures (MMRM) methodology with the unstructured variance covariance matrix. The model will include fixed class-effect terms for treatment, trial center, visit week, and an interaction term of treatment by visit week and include the interaction term of baseline values of ZAN-BPD total score by visit week as a covariate. Other continuous efficacy endpoints will also be analyzed using MMRM methodology.

[figure not shown]
Trial Duration:

Each subject in this trial is expected to participate in the following periods of the trial (approximate durations listed):

- Eligibility screening period (up to 21 days)
- Double-blind randomized treatment period (12 weeks)
- Post-treatment safety follow-up period (21 days; for subjects who do not enroll in the open-label extension trial)

Overall, the trial duration from first informed consent form signed to the final subject assessment is expected to be approximately 15.5 months.

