5.2 Handling of Missing Data

In general, missing data will be handled by analysis of mixed-effect model repeated measures (MMRM) methodology based on observed-case (OC) data from protocol-specified visits under the assumption of missing at random (MAR). The OC dataset consists of actual observations recorded at each visit and no missing data will be imputed.

The last observation carried forward (LOCF) analysis will include data recorded at a scheduled double-blind treatment phase visit or, if no observation is recorded at that visit, data carried forward from the previous scheduled double-blind treatment phase visit. Baseline data will not be carried forward to impute missing values for the LOCF analysis.

6 Study Conduct

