8.1.1 Primary Estimand

The primary estimand defining the treatment effect of interest in the trial uses the hypothetical strategy specified in the International Conference for Harmonisation (ICH) E9 (R1) Addendum. The objective of the primary analysis is to compare the efficacy of brexpiprazole versus placebo for the treatment of subjects with a diagnosis of BPD. The estimand, or target of estimation, following the hypothetical strategy is the pharmacological effect seen, had no withdrawals occurred. This hypothetical estimand is justifiable in this case, since the focus is on the pharmacological effect of the drug additional to non-specific effects. Subjects who withdraw from a symptomatic IMP treatment either could have lost their treatment effect, had the subjects not taken any other symptomatic medication after withdrawal, or could have their treatment effect been masked, had the subjects taken other symptomatic medication after withdrawal. This means that any observations taken after subjects stop IMP will most likely not contribute relevant information about the pharmacological effect of the drug. Due to this strategy, the last collected efficacy assessment after premature trial discontinuation will be done only once at the ET Visit. Every effort will be made to complete all of the ET evaluations prior to administering any additional medications for the treatment of BPD or other prohibited medications. In the case of terminal or lost to follow-up events no ET evaluations would be expected, and only scheduled assessments performed before such an event has occurred.

The primary estimand for this trial is defined by the following components:

- Target Population: FAS for Enriched Subjects
- Endpoint: Change from Baseline to Week 10 in the ZAN-BPD total score
- Intercurrent Events: Premature treatment discontinuation
- Measure of Intervention Effect: Difference in endpoint means between Brexpiprazole and Placebo arm.

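### SAP 8.4 tests CGI-I and PGI-C on LOCF data alone, while the other efficacy scores use a MAR-based MMRM; a MAR-based analysis should lead for these two supportive endpoints.

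*SAP*

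**What the plan says.** SAP 8.4 lists three secondary efficacy endpoints, each assessed at every double-blind visit. For the first, change in PGI-S: "Variable (1) will be evaluated using the same MMRM model described in the primary analysis". For PGI-C and CGI-I: "Variables (2) and (3) will be evaluated by the Cochran-Mantel-Haenszel (CMH) Row Mean Score Differ Test controlling, in last-observation-carried-forward (LOCF) analysis, for trial center". ZAN-BPD (8.1.2) and CGI-S (8.2) also use the MMRM.

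SAP 5.2 sets the general approach: "In general, missing data will be handled by analysis of mixed-effect model repeated measures (MMRM) methodology based on observed-case (OC) data", under MAR. Its next paragraph provides for the alternative: "The last observation carried forward (LOCF) analysis will include data recorded at a scheduled double-blind treatment phase visit or, if no observation is recorded", the score from the preceding scheduled visit. It adds: "Baseline data will not be carried forward to impute missing values for the LOCF analysis".

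SAP 8.1.1 aims at "the pharmacological effect seen, had no withdrawals occurred". It labels this the primary estimand and lists one endpoint for it: "Endpoint: Change from Baseline to Week 10 in the ZAN-BPD total score". No estimand is stated for CGI-I or PGI-C. The testing hierarchy in SAP 8.3 contains only the primary and key secondary endpoints.

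**The concern.** Two of the three secondary endpoints rest on a different missing-data assumption from the other efficacy scores, and SAP 8.4 gives no reason for it. LOCF sets a dropout's later scores equal to the last one recorded. MAR, which SAP 5.2, 8.1.1 and 8.1.4.1 adopt, lets later scores be predicted from the observed course, and that prediction need not be flat. If subjects are still improving when they leave, LOCF understates what they would have reached. If more leave from one arm, that arm is understated more.

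At stake is how to read these scores beside the primary result. If CGI-I or PGI-C disagrees with ZAN-BPD or PGI-S, the reader cannot tell a real difference between scales from an effect of the missing-data method. The MNAR analyses in SAP 8.1.4.1 are written for the primary analysis and do not cover this.

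**Working it through.** **Plan's own figure.** The plan gives no sample size or power for CGI-I or PGI-C. For the primary endpoint, SAP section 4 uses a difference of 2.6, SD 6.5, two-sided 0.05 and 80% power:

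n per arm = 2 × (1.960 + 0.842)² × (6.5/2.6)² = 2 × 7.85 × 6.25 = 98.1, so 99.

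With 100 per arm the power is 0.807. The stated 100 per arm reproduces, and it is used in step 2.

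**Inputs.**

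- From the documents: 5% non-evaluable or dropout rate and 100 evaluable per arm (SAP section 4); target days 7, 21, 35, 49 and 63 for Weeks 2 to 10 (SAP 10.1).
- Assumed, because the documents give nothing: linear improvement up to Week 10, the size of that improvement, every dropout rate other than 5%, and an SD of 1.2. Improvement on CGI-I is 4 (no change) minus the score.

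**Step 1. Share of a true difference that LOCF recovers.** Let an arm improve linearly to m at Week 10, with a fraction p leaving uniformly over time. Completers contribute m and dropouts m/2 on average:

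LOCF mean = (1 − p)m + p(m/2) = m(1 − p/2).

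With m = 1.9 (drug) and 1.5 (placebo), the true difference is 0.40.

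| Dropout, drug / placebo | LOCF mean, drug | LOCF mean, placebo | Difference | Share of 0.40 |
|---|---|---|---|---|
| 5% / 5% | 1.8525 | 1.4625 | 0.390 | 97.5% |
| 20% / 20% | 1.710 | 1.350 | 0.360 | 90% |
| 30% / 30% | 1.615 | 1.275 | 0.340 | 85% |
| 30% / 20% | 1.615 | 1.350 | 0.265 | 66% |
| 20% / 30% | 1.710 | 1.275 | 0.435 | 109% |

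Equal dropout shrinks the difference. Unequal dropout can shrink or enlarge it.

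**Step 2. Rejection rate with no true difference.** Both arms improve 1.5 points. The last visit of dropouts is spread evenly over the first four of the five visits at treatment weeks 1, 3, 5, 7 and 9. The mean share of improvement carried forward is (1 + 3 + 5 + 7)/(4 × 9) = 0.444, so each dropout loses 0.556 × 1.5 = 0.833 points on average.

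For 20% against 10% dropout:

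- Bias = 0.833 × (0.20 − 0.10) = 0.083.
- Standard error = 1.2 × √(2/100) = 0.170.
- Shift = 0.083/0.170 = 0.49 standard errors.
- Rejection = P(Z > 1.96 − 0.49) + P(Z < −1.96 − 0.49) = 0.071 + 0.007 = 0.078.

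The same steps give 5.0% at 5%/5%, 5.7% at 10%/5%, 11.4% at 30%/15% and 16.6% at 35%/15%. In the unequal cases the arm with more dropout looks worse. This is a two-sample z-test standing in for the center-stratified CMH test.

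**Step 3. Could the sign reverse?** In the step 1 model, with 20% placebo dropout, reversal needs 1.9(1 − p/2) < 1.35, which is drug-arm dropout above 58%. With 10% placebo dropout it needs 1.9(1 − p/2) < 1.425, which is above 50%.

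**The case against.** A reader might infer that SAP 8.4 contradicts the plan's own rules. The documents do not support that.

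- SAP 5.2 states a general rule and then defines LOCF, so 8.4 uses an exception that 5.2 provides for.
- The no-withdrawal estimand covers only the Week 10 ZAN-BPD change, so LOCF on other scores cannot breach it. The gap is that these two endpoints have no stated estimand.
- The protocol synopsis says "Other continuous efficacy endpoints will also be analyzed using MMRM methodology". CGI-I and PGI-C are 7-category change ratings, so that sentence does not clearly reach them. A row-mean-score test suits ordinal data, and neither score has a baseline value of its own for the MMRM's baseline term.

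A reader might also infer that dropouts are frozen at an early score, that the direction of effect is at risk, or that the two scores cannot corroborate the primary result. LOCF carries the last post-baseline score, which may be late. Early-termination ratings are mapped to visit windows, and only those more than 7 days after the last dose are excluded (SAP 10.1). A reversal needs the extreme imbalance in step 3. Moderate attenuation under equal dropout does not strip the scores of supportive value.

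The improvement and dropout patterns are assumptions, and the one planning rate in the SAP, 5%, gives a loss of only 2.5%. The documents give no dropout rate by arm. Protocol 2.3 reports TEAEs in 70.7% of brexpiprazole and 53.9% of placebo subjects, but that pools many trials, and an adverse event is not a withdrawal. The SAP's list of summary tables is not in the available text, so an observed-case table for these scores cannot be ruled out.

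All of this stands and limits the point. It does not make LOCF valid under MAR or supply a MAR-based test.

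**Conclusion.** The concern holds in limited form. CGI-I and PGI-C are tested on LOCF data, a method not generally valid under the assumption the SAP adopts elsewhere, and no MAR-based analysis of them appears in the available text.

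The size depends on dropout. It is negligible at 5% in each arm, about a 10% loss at 20% in each, and larger in either direction when the arms differ. Under no true difference the nominal 5% test reaches about 8% at 20% against 10%. These figures rest on linear improvement, evenly spread dropout and, for the rejection rates, SD 1.2 and 100 per arm.

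Both endpoints are outside the hierarchy in SAP 8.3, so no confirmatory conclusion depends on them. Minor severity; a cheap improvement.

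**What to change.** In SAP 8.4, state the estimand for CGI-I and PGI-C and make one MAR-based analysis the main one:

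- **CMH on multiply imputed data.** Keep the row-mean-score test by center and adapt the MAR imputation steps in Appendix 4. That code uses a baseline value and stops at Week 10. It would need baseline CGI-S (for CGI-I) or PGI-S (for PGI-C) as the starting variable, an extension to Week 12 if every visit is tested, and a stated rule for non-integer imputed scores. SAP 8.1.4.2 already plans to combine a rank-based CMH test over imputations.
- **MMRM on the visit score.** Use the terms in 8.1.2, with baseline CGI-S or PGI-S by visit as the covariate.

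Keep the LOCF CMH test as supportive. A CMH test on observed cases without imputation is not an adequate substitute, because it is not generally valid under MAR either.

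The cost is SAP wording and a little programming. If the MMRM is chosen, a 7-point ordinal score is treated as continuous, as the plan already does for CGI-S and PGI-S.

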9.1 Adverse Events

All adverse events will be coded by System Organ Class (SOC) and Preferred Term (PT) according to the Medical Dictionary for Regulatory Activities (MedDRA). AEs that are sexspecific, e.g., ovarian cancer, will have their incidence rates evaluated for the specific sex.

Treatment-emergent AEs (TEAEs) are defined as AEs with an onset date on or after the start of double-blind treatment period. In more detail, TEAEs are all adverse events which started after start of double blind IMP; or if the event was continuous from baseline and was

worsening, serious, study drug related, or resulted in death, discontinuation, interruption or reduction of study therapy. Adverse events occurring up to 30 days after the last day of IMP will be included in the summary tables.

The incidence of the following events in the double-blind treatment period will be tabulated by treatment group and overall using the Safety Sample:

- a) TEAEs
- b) TEAEs by severity
- c) TEAEs potentially causally related to the IMP
- d) TEAEs with an outcome of death
- e) Serious TEAEs
- f) TEAEs leading to discontinuations of the IMP
- g) AESI

The above summaries (b), (e) and (f) will also be prepared for TEAEs potentially causally related to the IMP.

In addition, incidence of TEAE during the double-blind treatment period of at least 5% in any treatment group other than placebo group, and also greater than placebo by SOC and PT will be provided.

Incidence of TEAEs by SOC and PT will be summarized for sex, race, age and region subgroups.

Extrapyramidal symptoms (EPS)-related AEs will be grouped into five categories.

- 1) Dystonic Events, which include cervical spasm, dystonia, emprosthotonos, muscle contractions involuntary, muscle rigidity, muscle spasms, muscle spasticity, myotonia, nuchal rigidity, oculogyration, opisthotonos, pleurothotonus, risus sardonicus, torticollis, and trismus;
- 2) Parkinsonian Events, which include akinesia, asterixis, athetosis, bradykinesia, cogwheel rigidity, essential tremor, extrapyramidal disorder, freezing phenomenon, gait festinating, hypertonia, hypokinesia, hypokinesia neonatal, intention tremor, masked facies, parkinson's disease, parkinsonian crisis, parkinsonian gait, parkinsonian rest tremor, parkinsonism, tremor, and tremor neonatal:
- 3) Akathisia Events, which include akathisia, hyperkinesia, and psychomotor hyperactivity;

- 4) Dyskinetic Events, which include ballismus, buccoglossal syndrome, choreoathetosis, clumsiness, dyskinesia, dyskinesia neonatal, dyskinesia oesophageal, fumbling, nodding of head, on and off phenomenon, and tardive dyskinesia;
- 5) Residual Events, which include chorea, Huntington's chorea, muscle twitching, and myoclonus.

Unless otherwise specified, in general, analysis of safety data will be performed on observed case and for last visit.

Adverse Events of Special Interest

The new onset or exacerbation of "Pathological Gambling and Other Compulsive Behaviors" will be analyzed as an AESI.

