1.1 Synopsis

Name of Sponsor: Otsuka Pharmaceutical Development & Commercialization, Inc.

Name of Investigational Medicinal Product: Brexpiprazole (OPC-34712)

Protocol No.: 331-201-00242

IND No.: 141091

Protocol Title: A Multicenter, Randomized, Flexible-dose, Double-blind Trial of Brexpiprazole Versus Placebo for the Treatment of Adults With Borderline Personality Disorder

Protocol Lay Person Short Title:

[figure not shown]
A Trial of Brexpiprazole in the Treatment of Borderline Personality Disorder

Clinical Phase/Trial Type: Phase 2 / Therapeutic confirmatory

Treatment/Indication: For the treatment of borderline personality disorder (BPD)

Objectives and Endpoints:

Trial Objectives and Endpoints	
Objectives	Endpoints
Primary: To compare the efficacy of brexpiprazole versus placebo for the	Primary efficacy: Change from baseline in the ZAN-BPD total score
treatment of subjects with a diagnosis of BPD	Key secondary efficacy: Change from baseline in the CGI-S score Secondary efficacy:
	 Change from baseline in the PGI-S for each trial visit during the double- blind treatment period
	PGI-C score
	CGI-I score

C-SSRS = Columbia-Suicide Severity Rating

Scale; Barnes Akathisia Rating Scale; ECG = electrocardiogram;

PGI-C = Patient's Global Impression of Change; PGI-S = Patient's Global

Impression of Severity; SAS = Simpson Angus Scale;

ZAN-BPD = Zanarini Rating Scale for Borderline Personality

Disorder.

Trial Design:

This will be a 12-week, multicenter, randomized, double-blind, placebo-controlled, 2-arm trial evaluating the efficacy and safety of brexpiprazole treatment in adult subjects with BPD. Subjects will be randomized (1:1) to 2-3 mg/day brexpiprazole (n = 120) or placebo (n = 120).

The trial will consist of a screening period (up to 21 days), a 12-week, double-blind treatment period, and safety follow-up (21 [±2] days after the last dose of investigational medicinal product [IMP]).

Trial Population:

Approximately 350 subjects will be screened to have 240 subjects randomized into the trial.

Key Inclusion Criteria:

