IMP accountability			X	X	X	X	X	X	X	
Schedule optional phone contact/other communication				X ^u						

anti-HCV = antibodies to hepatitis C virus; CCI

; ET = Early Termination;

FOCBP = females of childbearing potential; HBsAg = hepatitis B surface antigen; HIV = human immunodeficiency virus; IRE = immediately reported events; PGI-C = Patient's Global Impression of Change; PGI-S = Patient's Global Impression of Severity; PK = pharmacokinetic;

 T_4 = thyroxine.

^aExtension of screening may be requested and discussed with the medical monitor prior to the expiration of the screening period. Screening visit may be split over two days.

^bWeek designations correspond to the end of the week (eg, Week 4 visit occurs at the end of week 4 of the trial).

^cIf a subject discontinues early, every effort should be made to complete the "Week 12/End of treatment/ET" evaluations as soon as possible and, whenever possible, prior to starting any new medication or treatment.

^dTelephone contact or clinic visit (investigator's discretion) for evaluation of safety (AEs) for all subjects who do not enroll in the open-label extension trial.

^eAn assessment of all inclusion and exclusion criteria will be made to determine the subject's eligibility for the trial CCI . Subjects cannot be enrolled until site personnel have received the final CCI notification from the Medical Monitor or Clinical Scientist.

- ^fThe BPD and antisocial personality disorder modules must be conducted as part of screening in order to meet inclusion/exclusion criteria; however, per investigator discretion other PD modules may be administered at baseline in order to decrease the length of the screening visit. The investigator is responsible for determining that BPD is the primary personality disorder diagnosis at screening.
- ^gWashout of prohibited medications begins after completion of the consent process and must comply with the required washout periods (see Section 6.5).
- ^hTo include measurement of height (at screening only) and waist circumference.
- ¹Vital sign measurements include body weight, body temperature, systolic and diastolic blood pressure, and heart rate. Blood pressure and heart rate will be measured in the following order: supine and standing after the subject has been in each position for at least 3 minutes. Vital signs scheduled for the same visit as blood samples are to be completed before blood is drawn.

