- JBlood samples for clinical laboratory tests should be drawn after a minimum 8-hour fast at screening, if possible. If the Screening Visit laboratory samples were not obtained under fasting conditions, clinical laboratory tests (hematology, serum chemistry [including blinded prolactin], HbA1c, TSH with reflex to free T4 if the result for TSH is abnormal, and urinalysis) need to be obtained under fasting conditions at the Day 0 Visit. Vital sign and ECG assessments should be completed before any blood samples are collected.
- ^kStandard ECGs will be performed after the subject has been supine and at rest for ≥ 5 minutes prior to the ECG. Any screening ECG with abnormal result(s) considered to be clinically significant should be repeated to ensure reproducibility of the abnormality before excluding a subject. For ECG, perform 3 consecutive recordings. If 2 of the 3 remain exclusionary then the subject must be excluded.
- ¹All positive urine pregnancy test results must be confirmed by a serum test. Pregnancy tests can be performed at any point during the trial if pregnancy is suspected.
- ^mA urine drug screen and a blood alcohol test are required at the designated times, but either or both can be conducted at any time during the trial at the discretion of the investigator. See the exclusion criteria for exclusions based on urine drug screen and blood alcohol tests at screening.
- ⁿThe "Baseline/Screening" C-SSRS form will be completed for all subjects at screening to determine eligibility and the "Since Last Visit" C-SSRS form will be completed at the Day 0 Visit to ensure that the subject continues to qualify for the trial. The "Since Last Visit" C-SSRS form will also be completed at all visits after the Day 0 Visit.
- ^oAdverse events will be recorded starting after the subject completes the consent process and through the last scheduled trial visit (IREs will be collected through the last trial contact).
- ^pAll prescription and non-prescription therapy (pharmacological or other therapy) taken during the trial will be recorded. Details of prohibited therapies are provided in Section 6.5.1.
- ^qA PK sample will be collected at the same time of collection of clinical laboratory assessments, where applicable. Time of last 3 doses will be recorded at the time of PK sampling.

^tThe subject will be instructed to take their first dose of IMP during the Day 0 Visit.

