8.8.8.2 Follow-up of Immediately Reportable Events

This trial requires that subjects be actively monitored for IREs up to 21 days after the last dose of IMP is administered.

Immediately reportable events that are **identified or ongoing at the last scheduled contact** must be recorded as such on the AE eSource page and the IRE form. If updated information (eg, resolved status) on IRE status becomes available after a subject's last scheduled contact (up to last in-clinic visit for the entire trial), this must be reported to the sponsor and recorded on the AE eSource page and the IRE form, according to the appropriate reporting procedures described in Section 8.8.3.

It is expected that the investigator will provide or arrange appropriate supportive care for the subject and will provide prompt updates on the subject's status to the sponsor. The investigator will follow IREs until the events are:

- resolved,
- stabilized,
- the subject is lost to follow-up, or
- has died.

Resolution means that the subject has returned to the baseline state of health and stabilized means that the investigator does not expect any further improvement or worsening of the subject's condition. The investigator will continue to report any significant follow-up information to the sponsor up to the point the event has resolved or stabilized, or the subject is lost to follow-up, or has died.

Refer to Section 10.3 for additional information regarding the follow-up period for subjects that become pregnant or for pregnant partners of male subjects.

8.8.8.3 Follow-up and Reporting of Immediately Reportable Events Occurring After Last Scheduled Contact

Any new IREs reported to the investigator which occur after the last scheduled contact and are determined by the investigator to be reasonably associated with the use of the IMP, should be reported to the sponsor according to the procedures outlined in Section 8.8.3. This may include IREs that are captured on follow-up telephone contact or at any other time point after the defined trial period and continue to report any significant

Protocol 331-201-00242

follow-up information to the sponsor until the events are resolved or stabilized, or the subject is lost to follow-up or has died.

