Before trial enrollment, males and FOCBP must be advised of the importance of avoiding pregnancy during trial participation and the potential risk factors for an unintentional pregnancy. Subjects must sign the ICF confirming that the above-mentioned risk factors and the consequences were discussed.

A urine or serum pregnancy test for human chorionic gonadotropin will be performed at screening on all FOCBP. If a urine test is performed and is positive, the investigator will follow-up with a confirmatory serum test.

During the trial, all FOCBP should be instructed to contact the investigator immediately if they suspect they might be pregnant (eg, missed or late menstrual cycle). Male subjects must be instructed to contact the investigator immediately, during the trial, if their partner suspects that they might be pregnant (eg, missed or late menstrual cycle).

If a subject is suspected to be pregnant before she receives IMP, the IMP administration must be withheld until the results of serum pregnancy tests are available. If the pregnancy is confirmed, the subject must not receive the IMP and must not be enrolled in the trial. If pregnancy is suspected while the subject is taking IMP, the IMP must be withheld immediately (if reasonable, taking into consideration any potential withdrawal risks) until the result of the pregnancy test is known. If pregnancy is confirmed, the IMP will be permanently discontinued in an appropriate manner (eg, dose tapering if necessary for subject safety) and the subject will be withdrawn from the trial. Exceptions to trial discontinuation may be considered for life-threatening conditions only after consultations with the IRE contact (see the title page of this protocol for contact information).

The investigator must immediately notify the sponsor (within 24 hours) of any pregnancy associated with IMP exposure during the trial and for at least 30 days after the last dose of IMP, and record the event on the IRE form and forward it to the sponsor. The sponsor will forward the Pregnancy Surveillance Form(s) to the investigator for monitoring the outcome of the pregnancy.

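### SAP 9.1 tabulates adverse events to 30 days after the last dose, but the protocol schedules collection to day 21 (±2) at most, and only for subjects who do not enter the extension

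*SAP*

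**What the plan says.** **SAP 9.1 (Adverse Events):** "Adverse events occurring up to 30 days after the last day of IMP will be included in the summary tables". The next sentence describes the incidence tables as covering the double-blind treatment period, by treatment group, on the Safety Sample. The two statements are not reconciled. The section specifies incidence only. It gives no exposure adjustment, no split at the last dose and no cut-off at entry to the extension.

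**Protocol, when follow-up happens:** the synopsis (1.1) sets "safety follow-up (21 [±2] days after the last dose of investigational medicinal product [IMP", and its duration list repeats "Post-treatment safety follow-up period (21 days; for subjects who do not enroll in the open-label extension trial". Protocol 4.1 and SAP 3.1 also give 21 (±2) days and say that the contact applies to premature withdrawals.

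**Protocol, who is contacted and when recording stops:** Table 1.3-1 footnote d describes the contact as "for evaluation of safety (AEs) for all subjects who do not enroll in the open-label extension trial". Footnote o says that AEs are recorded from consent "through the last scheduled trial visit (IREs will be collected through the last trial contact".

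**Protocol, immediately reportable events (IREs) and pregnancy:** 8.8.8.2 requires that "subjects be actively monitored for IREs up to 21 days after the last dose of IMP is administered". Appendix 3 (10.3) requires notification "of any pregnancy associated with IMP exposure during the trial and for at least 30 days after the last dose of IMP".

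**Protocol, who may enter the extension:** Figure 1.2-1 footnote d and Section 6.6 limit the offer to subjects who complete all visits through Week 12.

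**The concern.** The treatment-emergent AE (TEAE) tables answer the secondary objective in SAP Section 2, safety and tolerability. A crude incidence compares arms fairly only if subjects in both arms are watched for comparable periods. Here the observed part of the post-dose window is set by whether a subject completes and then chooses the extension. Both can be influenced by treatment.

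One table in SAP 9.1 turns on a direct comparison: it keeps a term only if its incidence is at least 5% on brexpiprazole and higher than on placebo. Unequal observation could move a borderline term into or out of that table.

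The section also leaves the programmer to guess whether a post-treatment event belongs in a table labelled as double-blind treatment period.

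**Working it through.** The plan gives no derived figure to reproduce. The check is day arithmetic on the stated windows.

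**Inputs from the documents**
- Inclusion limit: 30 days after the last dose (SAP 9.1).
- Follow-up contact: 21 (±2) days, so day 19 to day 23 (Protocol 1.1 and 4.1; SAP 3.1).
- Recipients: subjects not entering the extension, including early withdrawals (Table 1.3-1 footnote d; Protocol 4.1).
- End of AE recording: last scheduled trial visit (Table 1.3-1 footnote o).
- Double-blind duration: 12 weeks = 84 days (Protocol 4.1) or 11 weeks = 77 days (SAP 3.1). The documents differ, so both are shown.

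**Step 1. Non-rollovers.** Unobserved days = 30 − contact day.
- Contact on day 19: 30 − 19 = 11 unobserved; 19/30 = 63% observed.
- Contact on day 21: 30 − 21 = 9 unobserved; 21/30 = 70% observed.
- Contact on day 23: 30 − 23 = 7 unobserved; 23/30 = 77% observed.

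**Step 2. Rollovers.** Footnote d gives them no follow-up contact, so under footnote o their last scheduled visit in this trial is Week 12. About 0 of the 30 days are observed. This is an inference from the two footnotes; no sentence says it outright.

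**Step 3. Total observation for a completer.**
- 84-day treatment: 84 + 21 = 105 days without rollover against 84 with it; 105/84 = 1.25.
- 77-day treatment: 77 + 21 = 98 against 77; 98/77 = 1.27.

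These figures apply to completers only. An early withdrawal is also a non-rollover and may be observed for less than either figure.

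**Step 4. How rollover changes observation by arm (assumed rates; the documents give none).** Mean observed post-dose days = 21 × (1 − rollover share), taking every non-rollover as contacted on day 21.
- 50% in both arms: 21 × 0.5 = 10.5 days each.
- 50% v 70%: 10.5 v 21 × 0.3 = 6.3 days.
- 30% v 70%: 21 × 0.7 = 14.7 v 6.3 days.

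With equal rollover the post-dose imbalance vanishes; with unequal rollover it does not.

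**Step 5. What part of a post-dose risk would be seen (assumed constant hazard).** For a true 30-day post-dose risk p, a contact on day 21 shows 1 − (1 − p)^(21/30).
- p = 5%: 3.5%.
- p = 10%: 7.1%.
- p = 20%: 14.5%.

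A rollover shows about 0% in each case.

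**The case against.** **The 30 days is a cap and promises no coverage.** This stands. Every AE collected by day 23 falls inside it, so no record is dropped. Changing 30 to 21 would alone change almost nothing. What remains is unequal observation inside the window and the conflict with the tables' stated period.

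**A reader might infer that no subject is observed to day 30.** The documents do not support that. Protocol 7.3.4 asks that subjects who have not fully withdrawn consent be followed for all specified evaluations if possible, so someone who stops treatment early may be seen beyond day 30. Protocol 8.8.8.3 allows later reporting of IREs judged associated with the drug. Neither gives systematic AE collection to day 30.

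**A reader might infer a bias of known direction.** Assume no drug effect, a constant hazard giving 54% incidence by day 77 (rate = −ln(0.46)/77 = 0.01008 per day) and rollover of 50% on placebo v 70% on brexpiprazole. If every non-rollover is observed for 98 days, incidence in that group is 62.8%. The arms then show 0.5 × 54 + 0.5 × 62.8 = 58.4% v 0.7 × 54 + 0.3 × 62.8 = 56.6%, an apparent placebo excess. But non-rollovers include dropouts. If half of them stop on day 35 and are observed to day 56 (incidence 43.1%), the arms show 0.5 × 54 + 0.25 × 62.8 + 0.25 × 43.1 = 53.5% v 0.7 × 54 + 0.15 × 62.8 + 0.15 × 43.1 = 53.7%. The sign reverses. All these rates are assumed, so neither result is an estimate for this trial.

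**A reader might infer that open-label events will be counted under placebo.** Protocol 6.6 treats the extension as a separate trial, and nothing says that its AEs are merged. The SAP merely lacks a rule that would exclude them if they were.

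**A reader might see pregnancy reporting as a plain contradiction.** Protocol 8.8.8.2 refers to Section 10.3 for pregnancy follow-up, and under 8.8.1 a normal pregnancy is not an AE, so the TEAE tables are unaffected. The 21-day and at-least-30-day statements still need to be reconciled, because 8.8.1 classes pregnancy as an IRE.

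**The table list may already separate post-treatment events.** SAP Section 13 was not in the text available for this review, so this cannot be judged. If it does, SAP 9.1 should say so.

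**Conclusion.** The mismatch is real and modest. SAP 9.1 admits AEs over a 30-day post-dose window that the protocol's schedule covers to day 19 to 23 for non-rollovers and, by inference, not at all for rollovers. The observed length depends on an event after randomisation that only completers can reach. Because the tables are crude incidences and SAP 9.1 does not split them at the last dose, the arm comparison can be distorted. The direction and size cannot be determined from the documents.

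The effect is confined to descriptive safety tables; no primary or key secondary test depends on it. Most TEAEs will probably arise on treatment, which limits the practical effect. The SAP's clause that its methods prevail over the protocol (SAP Section 1) settles which rule applies, but cannot supply events that were never collected.

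**What to change.** In SAP 9.1:
- Base the arm comparison, including the 5% table, on TEAEs with onset from the first to the last double-blind dose.
- Tabulate post-treatment events separately, for non-rollovers only, over the window that the protocol actually collects.
- Exclude events on or after the first open-label dose.
- Make the sentence naming the period of the tables agree with these rules.

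This needs SAP wording and one extra table, with no new data. The cost is slightly fewer events in the main table. It removes the dependence on rollover but not differences in time on treatment caused by dropout. It should be settled before treatment codes are opened, so that the AE window is not chosen after the results are seen.

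Separately, the sponsor should reconcile the 21-day IRE monitoring in Protocol 8.8.8.2 with the pregnancy notification period in Appendix 3. Which period applies is for the sponsor to decide.
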